#### **4.4.4 Procedures for handling patients incorrectly enrolled or randomised**

Patients who fail to meet the inclusion/exclusion criteria should not, under any circumstances, be enrolled or randomised. There can be no exceptions to this rule.

Where patients that do not meet the selection criteria are randomised in error or incorrectly started on treatment, or where patients subsequently fail to meet the study criteria post initiation, a discussion should occur between the AstraZeneca Study Team Physician and the Investigator regarding whether to continue or discontinue the patient from treatment. Once a decision is made, Investigators need to ensure they comply with all applicable requirements for human patient protection and ethical review.

The AstraZeneca Study Team Physician is to ensure all such decisions are appropriately documented. In situations where an agreement cannot be reached, the patient should have their study therapy stopped and be withdrawn from the study.

#### **4.4.5 Restrictions during the study**

Patients will be required to:

1. Not donate blood during the study and for 3 months following their last dose of trial treatment
2. Refrain from concomitant use of known inhibitors or inducers of CYP3A4 (see Section 4.5.10)
3. Refrain from taking any additional medication without the prior consent of the investigator
4. Refrain from drinking grape fruit juice while taking the study medication and for 3 months after the last dose of study medication

##### **4.4.5.1 Contraception**

Patients of child bearing potential and their partners, who are sexually active, must agree to the use of two highly effective forms of contraception throughout their participation in the study and for 3 months after last dose of study drug(s).

- Condom with spermicide

and one of the following

- Oral contraceptive or hormonal therapy (e.g. hormone implants)
- Placement of an intra-uterine device

Acceptable non-hormonal birth control methods include:

- Total sexual abstinence. Abstinence must be for the total duration of the study and the drug washout period.
- Vasectomised sexual partner plus male condom. With participant assurance that partner received post-vasectomy confirmation of azoospermia
- Tubal occlusion plus male condom with spermicide
- Intrauterine Device (IUD) plus male condom+spermicide. Provided coils are copper-banded

Acceptable hormonal methods:

- Etonogestrel implants (eg, Implanon, Norplan)+male condom with spermicide
- Normal and low dose combined oral pills+male condom with spermicide

- Norelgestromin/ethinyl estradiol (EE) transdermal system+male condom with spermicide
- Intravaginal device+male condom with spermicide (eg, EE and etonogestrel)
- Cerazette (desogestrel)+male condom with spermicide. Cerazette is currently the only highly efficacious progesterone based pill.

#### 4.4.5.2 Food intake restrictions

Patients should take AZD2281 no sooner than 1 hour after food. They should then refrain from eating for a further 2 hours due to potential effect of food on absorption. The olaparib capsules should be swallowed whole and not chewed, crushed, dissolved or divided.

See section 4.5.2 for further information.

#### 4.4.5.3 Other Concomitant treatment

1. No other chemotherapy, hormonal therapy (HRT is acceptable) or other novel agent is to be permitted during the course of the study for any patient (the patient can receive a stable dose of corticosteroids during the study as long as these were started at least 4 weeks prior to treatment, as per exclusion criteria above). Palliative radiotherapy is allowed for pre-existing small areas of painful metastases that cannot be managed with local or systemic analgesics as long as no evidence of disease progression is present (see Section 4.5.8).
2. Live virus and bacterial vaccines should not be administered whilst the patient is receiving study medication and during the 30 day follow up period. An increased risk of infection by the administration of live virus and bacterial vaccines has been observed with conventional chemotherapy drugs and the effects with olaparib are unknown.
3. Patients should avoid concomitant use of drugs, herbal supplements and/or ingestion of foods known to modulate CYP3A4 enzyme activity (see Section 4.5.6 from the time they enter the screening period until 30 days after the last dose of study medication. *In vitro* data have shown that the principal enzyme responsible for the formation of the 3 main metabolites of olaparib is CYP3A4 and consequently, this restriction is required to ensure patient safety.

#### 4.4.6 Discontinuation of Study Treatment

##### 4.4.6.1 Criteria for Discontinuation from Study Treatment

Patients may be discontinued from investigational product (IP) in the following situations:

- Patient decision. The patient is at any time free to discontinue treatment, without prejudice to further treatment

- Adverse event
- Severe non-compliance to study protocol
- Any CTCAE grade 3 or 4 events that have not reverted to CTCAE grade 1 or less within 28-days. At the Investigator's discretion, following dose interruption, patients may be considered for dose reductions. However, if upon re-challenging with AZD2281 at the lowest reduced dose, (for guidelines refer to Section 4.5.3), any CTCAE grade 3 or 4 adverse events recur, the patient must be discontinued.
- Bone marrow findings consistent with myelodysplastic syndrome/acute myeloid leukaemia
- Disease progression

Note: Patients may continue to receive study treatment following objective progression provided that, in the opinion of the Investigator, the patient is benefiting from the treatment and does not meet any other discontinuation criteria.

In the event that cisplatin is permanently discontinued on the basis of cisplatin related toxicity, treatment with AZD2281 alone may continue. If the patient does continue on AZD2281 alone, at the discretion of the PI and in consultation with AstraZeneca Study Team Physician, the patient may be dose escalated to receive the optimal monotherapy dose (i.e.: 400 mg bid).

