#### 4.5.3.4 Management of Hematologic NCI-CTCAE grade 3 or 4 AZD2281 Treatment Related Adverse Events

For the management for CTCAE grade 3 or 4 hematological toxicity, refer to Sections [4.5.3.1](#), [4.5.3.2](#), [4.5.3.3](#) and [Table 6](#).

**Table 6 Management of Hematologic (including Anaemic, Thrombocytopenic or Neutropenic) Grade 3 and 4 AZD2281 Treatment Related Adverse Events Whilst the Patient is Receiving Combination Therapy**

Initial Dose Level d	1 st Event Occurrence abe - Recommended Dose Reduction	2 nd Event Occurrence abe - Recommended Dose Reduction	Dose Administration
100 mg bid	50 mg bid	No reduction allowed – withdraw patient	Continuous
200 mg bid	100 mg bid	50 mg bid	Continuous
400 c mg bid	200 mg bid	100 mg bid	Continuous
50 mg bid	No reduction allowed – withdraw patient	Not applicable	Continuous
100 mg bid days 1-10 of a 21 day cycle	100 mg bid days 1-5 of a 21 day cycle	100 mg bid days 1-3 of a 21 day cycle	Intermittent
50 mg bid days 1-5 of a 21 day cycle	50 mg bid days 1-3 of a 21 day cycle	50 mg bid days 1-3 of a 21 day cycle Reduce cisplatin to 60 mg/m 	Intermittent

**Table 6 Management of Hematologic (including Anaemic, Thrombocytopenic or Neutropenic) Grade 3 and 4 AZD2281 Treatment Related Adverse Events Whilst the Patient is Receiving Combination Therapy**

Initial Dose Level d	1 st Event Occurrence abe - Recommended Dose Reduction	2 nd Event Occurrence abe - Recommended Dose Reduction	Dose Administration
50 mg bid <5 days dosing of a 21 day cycle	50 mg bid days 1-3 of a 21 day cycle Reduce cisplatin to 60 mg/m 	No reduction allowed – withdraw patient	Intermittent
50 mg bid days 1-5 dosing of a 21 day cycle with cisplatin dosed at 60 mg/m 	50 mg bid days 1-3 of a 21 day cycle Cisplatin dose to remain at 60 mg/m 	50 mg bid days 1-3 of a 21 day cycle Reduce cisplatin to 50 mg/m 	Intermittent
Dose schedule advised by safety monitoring committee	Patients on other dose schedules should have their dose decreased as appropriate in line with the above guidance		

a Hold any remaining doses of AZD2281 in the current cycle  
b Neutropenic events: Filgrastim or PEG-filgrastim may be implemented at the investigators discretion  
c If 400 mg bid dose is explored  

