d Initial dose level includes cisplatin dosed at 75mg/m^2 unless stated otherwise  
e At the investigators discretion, growth factor can be administered as required after the second dose of cisplatin

**Note:** The patient must be withdrawn if there is a third occurrence of any haematologic Grade 3 or 4 AZD2281 Treatment Related Adverse Events.

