#### 4.5.3.6 Management of Non-Hematologic NCI-CTCAE grade 3 or 4 AZD2281 Treatment Related Adverse Events

Treatment with AZD2281 must be interrupted for any non-hematologic CTCAE grade 3 or 4 adverse event which the Investigator considers to be related to administration of AZD2281. Repeated dose interruptions of up to a maximum of 28 days are allowed. Patients whose NCI CTCAE grade 3 or 4 event does not resolve to  $\leq$  grade 1 or to the baseline CTCAE grade after a full 28 day dose interruption should be withdrawn from the study.

Upon appropriate resolution of the toxicity (i.e., to NCI CTCAE grade 1 or to baseline CTCAE grade), the patient should restart treatment with AZD2281 but with a 50% dose reduction (as per [Table 7](#)). The dose of AZD2281 should not be reduced to less than 50 mg bid daily for patients receiving continuous AZD2281 dosing or to less than 50 mg bd for days 1-3 of a 21 day cycle for patients receiving intermittent AZD2281 dosing.

If the event recurs with the same severity, treatment should be interrupted again and, on resolution, a further dose reduction made where allowed.

Once a chemotherapy combination dose is reduced due to toxicity, combined chemotherapy dose re-escalation is not permitted.

**Table 7 Management of Non-Hematologica Grade 3 and 4 AZD2281 Treatment Related Adverse Events whilst the patient is receiving combination therapy**

Initial Dose Level c	1 st Event Occurrence - Recommended Dose Reduction	2 nd Event Occurrence – Recommended Dose Reduction	Dose Administration
100 mg bid	50 mg bid	No reduction allowed – withdraw patient	Continuous
200 mg bid	100 mg bid	50 mg bid	Continuous
400 b mg bid	200 mg bid	100 mg bid	Continuous
50 mg bid	No reduction allowed – withdraw patient	Not applicable	Continuous

**Table 7 Management of Non-Hematologica Grade 3 and 4 AZD2281 Treatment Related Adverse Events whilst the patient is receiving combination therapy**

Initial Dose Levelc	1st Event Occurrence - Recommended Dose Reduction	2nd Event Occurrence – Recommended Dose Reduction	Dose Administration
100 mg bid days 1-10 of a 21 day cycle	100 mg bid days 1-5 of a 21 day cycle	100 mg bid days 1-3 of a 21 day cycle	Intermittent
50 mg bid days 1-5 of a 21 day cycle	50 mg bid days 1-3 of a 21 day cycle	50 mg bid days 1-3 of a 21 day cycle Reduce cisplatin to 60 mg/m 	Intermittent

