50 mg bid <5 days dosing of a 21 day cycle	50 mg bid days 1-3 of a 21 day cycle Reduce cisplatin to 60 mg/m 	No reduction allowed – withdraw patient	Intermittent
50 mg bid days 1-5 dosing of a 21 day cycle with cisplatin dosed at 60 mg/m 	50 mg bid days 1-3 of a 21 day cycle Cisplatin dose to remain at 60 mg/m 	50 mg bid days 1-3 of a 21 day cycle Reduce cisplatin to 50 mg/m 	Intermittent
Dose schedule advised by safety monitoring committee	Patients on other dose schedules should have their dose decreased as appropriate in line with the above guidance		

a With the exception of grade 3 or worse neurologic toxicity, in which case both cisplatin and AZD2281 should be discontinued, as per Section 4.5.3.8

b If 400 mg bid dose is explored

c Initial dose level includes cisplatin dosed at 75mg/m^2 unless stated otherwise

**Note:** The patient must be withdrawn if there is a third occurrence of any non-haematologic Grade 3 or 4 AZD2281 Treatment Related Adverse Events.

**4.5.3.7 Management of Non-Hematologic NCI-CTCAE grade ≤2 AZD2281 Treatment Related Adverse Events whilst the patient is receiving combination therapy**

For non-hematologic toxicities of CTCAE grade ≤2 that the investigator feels are related to the administration of AZD2281, the investigators should use their discretion in deciding whether dose interruptions are necessary and should also treat the events as medically appropriate based on signs and symptoms.

Except as noted above, the dose of AZD2281 must not be modified under any other circumstances unless prior agreement is given by AstraZeneca Pharmaceuticals.

*Management of new or worsening pulmonary symptoms:* If new or worsening pulmonary symptoms (e.g. dyspnoea) or radiological abnormality occurs, an interruption in AZD2281 dosing is recommended and a diagnostic workup (including a high resolution CT scan) should be performed, to exclude pneumonitis. Following investigation, if no evidence of abnormality is observed on CT imaging and symptoms resolve, then AZD2281 treatment can be restarted, if deemed appropriate by the investigator. If significant pulmonary abnormalities are identified, these need to be discussed with the AstraZeneca Study Physician.

All dose reductions and/or interruptions (including any missed doses), and the reasons for the reductions and/or interruptions are to be recorded in the CRF.

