Other clinically significant grade $\geq 3$ toxicities	Hold up to 28 days until recovery to $\leq$ grade 1 or baseline if considered possibly related; reduce dose as per Table 7. After resumption, if toxicity returns interrupt. If toxicity does not recover to $\leq$ grade 1, discontinue AZD2281. The minimum dose of AZD2281 is 50 mg bid days 1-3 of a 21 day cycle for patients treated with intermittent dosing and 50 mg bid for patients treated with continuous dosing.	Hold up to 14 days until recovery to $\leq$ grade 1 or baseline if considered possibly related; may resume at current dose or with dose reduction, to a minimum of 60 mg/m  , per the Investigator’s discretion
Grade 4 non-hematologic toxicities attributable to cisplatin	No change unless cisplatin is discontinued. If cisplatin is discontinued, at the investigators discretion and if treatment criteria are met, dose of AZD2281 can be escalated to 400 mg bid continuously.	Discontinue cisplatin. If the investigator believes that the patient is benefiting from combination therapy then reducing cisplatin to 50 mg/m  and maintaining the dose of AZD2281 may be considered instead of the above after discussion with the Principal Investigator and agreed by AstraZeneca.

a The dose reductions advised in the table relate to patients who had an initial cisplatin dose of 75mg/m^2, for those patients that had their initial cisplatin dose administered at 60 mg/m^2, the dose modification of cisplatin should be a reduction to 50 mg/m^2 per the Investigator’s discretion.

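### Section 4.4.6.1 stops a patient whose Grade 3-4 toxicity recurs at the lowest reduced AZD2281 dose; two intermittent rows of Tables 6 and 7 keep that patient on treatment

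*Protocol*

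**What the plan says.** **Section 4.4.6.1** allows dose reduction after a Grade 3-4 event and then sets a limit: "However, if upon re-challenging with AZD2281 at the lowest reduced dose, (for guidelines refer to Section 4.5.3", and, in the same sentence, "any CTCAE grade 3 or 4 adverse events recur, the patient must be discontinued". The dose named is that of AZD2281, and Section 4.5.3 is cited for it.

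**Section 4.5.3** gives the AZD2281 minimum twice. Section 4.5.3.6 says that the dose should not go below 50 mg bid for continuous dosing, nor "to less than 50 mg bd for days 1-3 of a 21 day cycle for patients receiving intermittent AZD2281 dosing". Table 8 repeats it: "The minimum dose of AZD2281 is 50 mg bid days 1-3 of a 21 day cycle for patients treated with intermittent dosing".

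**Tables 6 and 7** (haematological and non-haematological events) give identical steps for a first and a second AZD2281-related Grade 3-4 event. For a start at 50 mg bid on days 1-5 with cisplatin 75 mg/m², the second-event entry is "50 mg bid days 1-3 of a 21 day cycle Reduce cisplatin to 60" mg/m². The note to Table 6 reads "The patient must be withdrawn if there is a third occurrence of any haematologic Grade 3 or 4" AZD2281-related event; the note to Table 7 reads "The patient must be withdrawn if there is a third occurrence of any non-haematologic Grade 3 or 4".

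**Bans on increases.** Section 4.5.3.6 says "Once a chemotherapy combination dose is reduced due to toxicity, combined chemotherapy dose re-escalation is not permitted". Section 4.1.1 also rules out escalation within a patient on combination therapy.

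**The concern.** An investigator whose patient has a severe toxicity again at the minimum AZD2281 dose needs one answer. For two starting regimens the protocol gives two: stop (Section 4.4.6.1), or continue with less cisplatin (Tables 6 and 7). One of them, 50 mg bid on days 1-5 with cisplatin 75 mg/m², is the fallback named in the synopsis and Section 4.1 should the first intermittent cohort not be tolerated.

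This is first a patient-safety matter. It also bears on the primary objective, safety and tolerability. Which section a site follows changes who is taken off treatment for toxicity, and it can change who reaches the four completed cycles required of six evaluable patients in the expanded cohort.

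**Working it through.** The plan states no figure to reproduce. The check walks each starting regimen through the tables and compares the AZD2281 dose with the stated minimum (50 mg bid continuous; 50 mg bid days 1-3 intermittent). Doses are mg bid; "cis" is cisplatin in mg/m², 75 unless shown.

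**Step 1: one class of toxicity.**

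| Start | After 1st event | After 2nd event | Against Section 4.4.6.1 |
|---|---|---|---|
| 50 continuous | withdraw | not applicable | no conflict |
| 100 continuous | 50 (minimum) | withdraw | agrees |
| 200 continuous | 100 | 50 (minimum); 3rd event withdraws | agrees |
| 400 continuous | 200 | 100; 3rd event withdraws | minimum never reached |
| 100 days 1-10 | 100 days 1-5 | 100 days 1-3; 3rd event withdraws | minimum never reached |
| 50 days 1-5 | 50 days 1-3 (minimum) | 50 days 1-3, cis 60; 3rd event withdraws | **conflict at 2nd event** |
| 50, fewer than 5 days (taken as days 1-3) | 50 days 1-3, cis 60 | withdraw | no conflict |
| 50 days 1-5, cis 60 | 50 days 1-3 (minimum), cis 60 | 50 days 1-3, cis 50; 3rd event withdraws | **conflict at 2nd event** |

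In the two conflicting rows the AZD2281 amount per cycle is 2 × 50 × 5 = 500 mg at the start, 2 × 50 × 3 = 300 mg after the first event, and still 300 mg after the second. The second event is therefore a recurrence at the AZD2281 minimum, yet treatment goes on. In the 100 mg continuous row the same tables withdraw the patient in that situation, so the tables also differ among themselves.

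**Step 2: which events count.** Section 4.4.6.1 refers to any Grade 3-4 event. Tables 6 and 7 are limited by title and notes to AZD2281-related events. A recurrent Grade 3-4 event judged unrelated falls under the first and outside the second.

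**Step 3: mixed toxicities.** Each table counts its own class and looks up the dose from the initial level. Take two haematological events, then a first non-haematological one (the reverse order gives the same), and read the entries literally:

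- 200 continuous: 200 → 100 → 50, then the entry is 100.
- 400 continuous: 400 → 200 → 100, then the entry is 200.
- 100 days 1-10, per cycle: 2 × 100 × 10 = 2000 mg → 1000 mg → 600 mg, then the entry is 1000 mg.
- In the two 50 mg days 1-5 rows AZD2281 stays at the minimum, but the first-event entry implies cisplatin at its starting dose (75 or 60) after it had been lowered (to 60 or 50).

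Sections 4.1.1 and 4.5.3.6 forbid an increase, so in these sequences the table entry cannot be applied and no other entry is given.

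A further case involves no increase. A patient who started at 100 mg continuous is at 50 mg after one haematological event and then has a first non-haematological event. Table 7 reads 50 mg bid, so the patient continues at the minimum. Whether Section 4.4.6.1 stops this patient depends on whether a first event of another class counts as a recurrence, which is not stated.

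**The case against.** **The lowest reduced dose could mean the last step of the patient's table row, cisplatin included.** Section 4.4.6.1 does point to Section 4.5.3, and on that reading the third-occurrence notes would agree with it. But the sentence names AZD2281 alone, and Section 4.5.3.6 and Table 8 define an AZD2281 minimum. The reading is possible but does not fit the words, and a site should not have to find it.

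**The sentence sits under a permissive opening, in the bullet on events unresolved after 28 days.** True, but the sentence itself is mandatory and refers to the general toxicity section. Nothing says that the tables take precedence.

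**Most rows are consistent.** This stands. With one class of toxicity, six of the eight explicit rows withdraw the patient or never reach the minimum before the third event. The point is confined to the other two.

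**A reader might infer that the protocol lets the dose be raised after mixed toxicities.** It does not. The columns are headed as dose reductions, and Sections 4.1.1 and 4.5.3.6 forbid escalation and re-escalation on combination therapy. What is left is a missing instruction.

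**A reader might infer that a patient can always have four Grade 3-4 events, two per class, before withdrawal.** Three rows (100 mg continuous, 50 mg continuous, and 50 mg for fewer than five days) withdraw at the first or second event of a class. Elsewhere it needs separate counts and Section 4.4.6.1 set aside.

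**Conclusion.** The contradiction is real and narrow: two of eight explicit rows in each of Tables 6 and 7 keep a patient on treatment where Section 4.4.6.1 requires discontinuation. It rests on reading the lowest reduced dose as the AZD2281 minimum in Section 4.5.3.6 and Table 8, which the wording supports. The mismatch in which events count and the unstated handling of mixed toxicities are ambiguities that should be closed at the same time.

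The number of patients affected cannot be derived. Table 3 plans 4-12 patients for each of the two cohort options, but these are conditional and are whole cohort sizes. Only a patient with a further Grade 3-4 event at the minimum is touched, and there may be none. A reader might also size the relatedness gap from Section 2, where 31/57 (54.4%) had any Grade 3 or higher event and 14/57 (24.6%) a related one. Those are incidences in a monotherapy study, and they say nothing about recurrence at the lowest dose with cisplatin.

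No effect on the MTD is shown, since DLTs are confined to Cycle 1. The weight of the point lies in patient safety and in consistent tolerability data.

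**What to change.** Reconcile Section 4.4.6.1 with Tables 6 and 7, their notes, Section 4.5.3.6 and Table 8, so that three things read the same in all places:

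1. What the lowest reduced dose is for each starting regimen, and whether a cisplatin reduction is part of it.
2. Whether the events that count are any Grade 3-4 events or only those related to AZD2281.
3. How haematological and non-haematological events combine: whether they share one count, whether a first event of the other class is a recurrence, and what applies when the table entry lies above the dose being taken.

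The clinical team chooses the rule in each case. The cost is an amendment of wording in these places, with no added patients, visits or assessments.

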#### **4.4.6.2 Procedures for Discontinuation of a Patient from Investigational Product**

A patient that decides to discontinue investigational product will always be asked about the reason(s) and the presence of any adverse events. If possible, they will be seen and assessed by an Investigator(s). Adverse events will be followed up (See Sections 5.10.3 and 5.10.4); and all study drugs should be returned by the patient.

Any patient discontinuing investigational product should be seen at 30 days post discontinuation of study treatment for the evaluations outlined in the study schedule. The patient's tumour status should be assessed clinically and, if appropriate, disease progression should be confirmed by radiological assessment. After discontinuation of study medication, the principal Investigator/Sub-Investigator will perform the best possible observation(s), test(s) and evaluation(s) as well as give appropriate medication and all possible measures for the safety of the patient. In addition, they will record on the CRF the date of discontinuation, the reasons, manifestation and treatment at the time of discontinuation. If patients discontinue study treatment, the AstraZeneca monitor must be informed immediately. Patients will be required to attend the treatment discontinuation visit. The patient should return all study medication.

After discontinuation of the study medication at any point in the study, all ongoing AEs or SAEs must be followed until resolution unless, in the Investigator's opinion the condition is unlikely to resolve due to the patients underlying disease, or the patient is lost to follow up

(see Sections 5.10.3 and 5.10.4). All new AEs and SAEs occurring during the 30 calendar days after the last dose of study medication must be reported (if SAEs, they must be reported to AstraZeneca within 24 hours as described in Section 5.10.4) and followed to resolution as above. Patients should be seen at least 30 days after discontinuing study medication to collect and /or complete AE information. Any untoward event occurring subsequent to the 30-day follow-up AE reporting period that the investigator assesses as possibly related to the study medication should also be reported as an AE.

